1. PROTOCOL SYNOPSIS FOR STUDY 201842

Rationale

Primary Sjögren's syndrome (pSS) is a common autoimmune disease characterized by oral and ocular dryness as well as systemic manifestations. B cells are thought to play a central pathogenic role. There are no disease modifying treatments for this disease and existing approved therapies consist of symptomatic treatments that do not address the autoimmune pathology. Therefore, substantial unmet medical need exists for a disease modifying therapy; one that can stop B-cell mediated autoimmune damage, alleviate glandular as well as constitutional symptoms, and ameliorate extra-glandular target organ manifestations.

Clinical studies suggest that targeting B-cells with belimumab or rituximab may improve disease symptoms of patients with Sjögren's syndrome. In addition, scientific evidence suggests that dual B-cell targeted immunotherapy with both B lymphocyte stimulator (BLyS) blockade (i.e., belimumab) and B cell depletion (i.e., rituximab; anti-CD20) may be more efficacious than targeting either mechanism alone. Therefore, this proof of mechanism study will assess whether either dual B-cell immunotherapy (i.e., co-administration of belimumab and rituximab) or belimumab monotherapy demonstrates a favorable safety and tolerability profile and results in improvements in clinical status, functional outcomes and mechanistic endpoints in comparison to placebo or rituximab monotherapy.

Overall Design

The primary efficacy comparison for this study at Week 24 will be between the co-administration therapy arm and the placebo arm. Once approximately 35 subjects have

completed week 24, a formal interim analysis will be performed on the available data. Following this interim analysis, a number of actions could be taken: the study could continue as planned; one or more treatment arms may be dropped; the number of subjects in some or all treatment arms may be increased following sample size re-estimation up to a maximum of 120 total subjects in the study.

Key Objective(s)/Endpoint(s)

Objectives	Endpoints
Primary	

 Safety and tolerability of anti-BLyS / anti-CD 20 co-administration therapy and anti-BLyS and anti-CD 20 monotherapies 	
 Safety and tolerability; including incidence of SAEs and AESIs
Secondary	

 Clinical efficacy of anti-BLyS / anti-CD 20 co-administration therapy and anti-BLyS and anti-CD 20 monotherapies Assessment of anti-BLyS / anti-CD 20 co-administration therapy and anti-BLyS and anti-CD 20 monotherapies on tissue B-cells 	
 ESSDAI score over time Stimulated salivary flow over time Oral dryness numeric response scale over time B cell quantification within salivary gland biopsy at Week 24
Exploratory	

 Assessment of mechanism and durability of effect of anti-BLyS/anti-CD 20 co-administration therapy and anti-BLyS and anti-CD20 monotherapies 	
 Sustained efficacy of anti-BLyS/anti-CD 20 co-administration at Week 52 Extended mechanistic assessment of anti-BLyS/anti-CD20 co-administration and monotherapies in blood, tissue and saliva at Week 24 and 52

Treatment Arms and Duration

Approximately 70 subjects will be recruited into the study initially. At Day 0, subjects will be randomized 1:2:2:2 to one of the four treatment arms below.

1. Placebo Arm: Approximately 10 subjects will receive belimumab placebo weekly subcutaneous injections to Week 52 and rituximab placebo infusions at Weeks 8 and 10.

2. Belimumab Monotherapy Arm: Approximately 20 subjects will receive 200 mg weekly subcutaneous injections of belimumab to Week 52 and placebo rituximab infusions at Weeks 8 and 10.
3. Co-administration Therapy Arm: Approximately 20 subjects will receive belimumab 200 mg weekly subcutaneous injections for 24 weeks followed by weekly placebo belimumab injections to Week 52 with rituximab 1,000 mg intravenously at Weeks 8 and 10.
4. Rituximab Monotherapy Arm: Approximately 20 subjects will receive 1,000 mg IV rituximab infusions at Weeks 8 and 10 and weekly subcutaneous injections of placebo belimumab to Week 52.

General Follow up Period

Subjects in all arms will receive investigational product (IP) until Week 52 (completion of the treatment phase). All subjects will enter a 16-week general follow-up period after the Week 52 visit or after discontinuation, if a subject discontinues IP and withdraws from the treatment phase visits prior to Week 52.

Individualized Follow up Period

After completing the general follow-up period, subjects with CD19+ B-cell levels below the lower limit of normal (LLN) (or less than 90% of baseline, if baseline value was below LLN) will enter an individualized safety follow-up phase and return to the clinic for visits every 12 weeks up to a maximum of two years (i.e., up to Week 104).

Type and Number of Subjects

Adult subjects with symptomatic and systemically active disease as well as evidence of glandular reserve function will be recruited. Initially, approximately 70 subjects will be randomized. Withdrawn subjects may be replaced, and there is potential to further increase the number of subjects in one or more arms following sample size re-estimation, up to a maximum of 120 recruited into the study. The randomization ratio will vary dependent on the number of treatment arms continuing following the interim analysis

Analysis

Hypotheses and Treatment Comparisons: The primary objective of the study is to investigate the safety and tolerability of the co-administration of belimumab with rituximab and of belimumab monotherapy. No formal statistical comparisons will be conducted to assess this objective. If deemed appropriate, to investigate the secondary efficacy and mechanistic endpoints, the following comparisons may be conducted:

- Co-administration belimumab/rituximab treatment arm vs. Placebo arm
- Co-administration belimumab/rituximab treatment arm vs. Rituximab monotherapy arm

- Co-administration belimumab/rituximab treatment arm vs. Belimumab monotherapy arm
- Belimumab monotherapy arm vs. Placebo arm
- Belimumab monotherapy arm vs. Rituximab monotherapy arm

If deemed appropriate, these exploratory comparisons will be made investigating ESSDAI score, stimulated salivary flow, oral dryness numeric response scale and a subset of salivary gland histology assessments and B cell quantification. For all other parameters, no formal statistical comparisons will be made, although trends over time will be investigated across all treatment arms.

Sample Size Calculations: Initially approximately 70 subjects will be recruited into the study. The study is not powered to detect pre-defined differences.

Interim Analysis: Once half of the planned subjects (i.e.: approximately 35 subjects) have completed their Week 24 assessments, a formal interim analysis will take place. Appropriate available safety and efficacy data will be included in the interim analysis. The main purpose of the interim analysis is to assess the safety and tolerability of the study drugs. In addition, preliminary efficacy analysis may be conducted. to enable a sample size re-estimation and obtain an initial estimate of the effect size of the co-administration therapy and belimumab monotherapy. Following the interim analysis, a number of actions could be taken: the study may continue as planned; one or more treatment arms may be dropped; the number of subjects in some or all treatment arms may be increased following sample size re-estimation, up to a maximum of 120 subjects in the study

Data Analysis Considerations: All data will be descriptively summarized, graphically presented and listed appropriately. The relationship between the mechanistic endpoints (e.g., salivary gland B cell quantification) and clinical effects (e.g., ESSDAI score) will be graphically presented. The consistency in the changes over time between the endpoints will be assessed and further exploratory analyses to characterize relationships between endpoints may be conducted. Comparisons between treatment groups will be conducted if deemed appropriate. For example, the change from baseline in ESSDAI score will be statistically analyzed using a mixed effect model repeated measurement (MMRM) analysis comparing the co-administration with placebo at each time point. Similar analyses may be conducted for other secondary endpoints. In addition, based on the data that we observe in the study, probabilities of success may be determined, for example, what is the probability that we would observe a certain change in ESSDAI score (i.e., comparator rate), based on the data that we have observed in the study?

2. INTRODUCTION

2.1. Study Rationale

Primary Sjögren's syndrome (pSS) is a common autoimmune disease characterized by oral and ocular dryness as well as systemic manifestations. B cells are thought to play a central pathogenic role. There are no disease modifying treatments for this disease and existing approved therapies consist of symptomatic treatments that do not address the autoimmune pathology. Therefore, substantial unmet medical need exists for a disease modifying therapy; one that can stop B-cell mediated autoimmune damage, alleviate glandular as well as constitutional symptoms and ameliorate extra-glandular target organ manifestations.

Clinical studies suggest that targeting B-cells with belimumab or rituximab may improve disease symptoms of patients with Sjögren's syndrome. In addition, scientific evidence suggests that dual B-cell targeted immunotherapy with both B lymphocyte stimulator (BLyS) blockade (i.e., belimumab) and B cell depletion (i.e., rituximab) may be more efficacious than targeting either mechanism alone. Therefore, this proof of mechanism study will assess whether either dual B-cell immunotherapy (i.e., co-administration of belimumab and rituximab) or belimumab monotherapy demonstrates a favorable safety and tolerability profile and results in improvements in clinical status, functional outcomes and mechanistic endpoints in comparison to placebo or rituximab monotherapy.

2.2. Brief Background

Sjögren's syndrome is manifest by sicca symptoms, constitutional findings, and potentially severe, life-threatening organ-specific extra-glandular manifestations. It is characterized by a combination of features including oral and ocular dryness, which can be disabling; ocular signs including objective evidence for involvement; salivary gland involvement including abnormal appearance of salivary glands; and presence of antibodies to Ro and/or La. Patients may also experience severe, variable and unpredictable fatigue, which is similar in character and severity to that of patients with systemic lupus erythematosus (SLE). Similarly, fibromyalgia and widespread chronic pain are found in 5% of pSS patients, again, comparable to SLE. Extra-glandular manifestations occur in 20 to 40% of patients and include rashes, peripheral neuropathy, Hashimoto's thyroiditis, non-erosive arthritis, arthralgia, vasculitis, interstitial lung disease, B-cell lymphoma, pancreatitis, primary biliary cirrhosis, autoimmune hepatitis and renal disease.

BLyS (also known as BAFF) promotes B-cell maturation, proliferation and survival. Transgenic mice that over-express this cytokine develop features of SLE, and go on to develop clinical characteristics of primary Sjögren's syndrome [Mackay, 1999]. In recent years, several studies have focused on elucidating the role of BLyS in primary Sjögren's syndrome. Serum BLyS levels were demonstrated to be increased, and to correlate with, levels of anti-Ro/SS-A antibodies and rheumatoid factor (RF) in patients with primary Sjögren's syndrome [Mariette, 2003] and elevated levels of BLyS have been detected in saliva [Daridon, 2007; Lavie, 2008].

Belimumab, an anti-BLyS therapy, has been studied in patients with Sjögren's syndrome. In the open label, Phase II BELISS trial of belimumab in patients (n = 30) with primary Sjögren's syndrome, 60% of subjects (18/30) met the primary endpoint - improvement in at least two of the following five parameters: dryness, fatigue, pain, systemic activity or B-cell biomarkers - measured at 28 weeks [Mariette, 2015]. This study will allow the opportunity to test the efficacy of belimumab in a placebo controlled, randomized trial and will extend the observations of the BELISS study in assessing the effects on disease activity in patients treated with belimumab for 12 months.

Rituximab, an anti-CD 20 therapy, has also been studied in patients with Sjögren's syndrome. In general, these studies - despite being heterogenous, especially with respect to the patient populations recruited - have shown evidence of temporary beneficial effects on symptoms of dryness and fatigue [Meijer, 2010; Devauchelle-Pensec, 2014; Dass, 2008]. Furthermore, additional studies have raised the possibility of rituximab positively impacting systemic disease, salivary histology and biomarkers such as beta2 microglobulin [Carubbi, 2014]. As a result, rituximab has been recommended as a potential treatment [Ramos-Casals, 2012] in subjects with systemic disease.

Administration of anti-CD20 therapy has been shown to result in an increase in serum BLyS [Cambridge, 2006; Lavie, 2007; Pers, 2007]. This increase is linked both to the disappearance of BLyS-binding B cells in peripheral blood, as well as to a true homeostatic feedback characterized by increased BLyS mRNA expression in monocytes after rituximab [Toubi, 2007; Lavie, 2007]. This increase in BLyS after rituximab could favor the stimulation of new autoimmune B cells and, possibly explains the waning clinical improvement over time seen in clinical studies of rituximab in patients with Sjögren's syndrome.

Anti-BLyS and anti-CD20 therapeutics operate through different but complementary mechanisms: anti-BLyS (e.g., belimumab) therapeutics rapidly increase peripheral memory B cells (possibly by mobilization/redistribution of tissue B cells), decrease naive, activated and plasma B cell subsets, and increase stringency on B cell selection during reconstitution; while anti-CD20 (e.g., rituximab) therapeutics eliminate peripheral B cells through complement dependent cytotoxicity (CDC) and antibody-dependent cell-mediated cytotoxicity (ADCC). Paired together, these two mechanisms may achieve synergistic effects through improved depletion of memory and germinal center tissue B cells and increased stringency during B cell reconstitution with additive effects through more efficient targeting of circulating plasma cells.

3. OBJECTIVES AND ENDPOINTS

Objectives	Endpoints
Primary	

 Safety and tolerability of anti-BLyS / anti-CD 20 co-administration therapy and anti-BLyS and anti-CD 20 monotherapies 	
 Safety and tolerability; including incidence of SAEs and AESIs.
Secondary	

 Clinical efficacy of anti-BLyS / anti-CD 20 co-administration therapy and anti-BLyS and anti-CD 20 monotherapies Assessment of anti-BLyS / anti-CD 20 co-administration therapy and anti-BLyS and anti-CD 20 monotherapies on tissue B-cells. 	
 ESSDAI score over time Stimulated salivary flow over time Oral dryness numeric response scale over time B cell quantification within salivary gland biopsy at Week 24

Objectives	Endpoints
Exploratory 
 Assessment of mechanism and durability of effect of anti-BLyS/anti-CD 20 co-administration therapy and anti-BLyS and anti-CD20 monotherapies. 	
 Ocular dryness numeric response scale over time Lacrimal gland function as measured by Schirmer's test. Physician's Global Assessment (PGA) of disease activity over time Serologic markers over time Change in peripheral blood leukocytes including B cell subsets over time BLyS levels in blood Immunogenicity of rituximab and belimumab Pharmacokinetics of rituximab and belimumab Change from baseline in the cellular composition of the salivary gland Sustained efficacy of anti-BLyS/anti-CD 20 co-administration at Week 52 Additional exploratory biomarkers may be evaluated 
 Transcriptomic analysis of blood and salivary gland B and T cell receptor clonal analysis in peripheral blood and salivary gland Proteomic assessment of the saliva
Health Outcomes 
 Gather preliminary information on patient reported outcomes of anti-BLyS/anti-CD 20 co-administration therapy and anti-BLyS and anti-CD 20 monotherapies 	
 ESSPRI score (and individual scale subscores) over time Fatigue and Discomfort- SICCA Symptom Inventory (PROFAD SSI SF) over time Patient Global Assessment (PtGA) of disease activity over time Subject exit interviews

4. STUDY DESIGN

4.1. Overall Design

This will be a multi-national, multi-center, double-blind (sponsor open) (see Section 6.3), randomized, placebo-controlled trial in subjects with active primary Sjögren's syndrome. The study design is shown in the schematic above.

This study is designed to understand the safety and tolerability profile of belimumab/rituximab co-administration and of belimumab monotherapy; and to evaluate whether either co-administration therapy or belimumab monotherapy has a substantive effect on disease activity. It is also designed to understand the underlying immunological mechanisms impacted by belimumab monotherapy compared to placebo or rituximab monotherapy and to determine if there is a mechanistic difference between monotherapy and co-administration therapy. Disease activity assessment at Week 52 will allow determination of whether any clinical effects of co-administration therapy achieved at Week 24 are sustained after discontinuation of therapy and/or whether chronic treatment with belimumab monotherapy is effective.

Study data will be reviewed in a confidential manner during the conduct of the trial. In line with routine pharmacovigilance, subjects' blinded safety data will be reviewed on an ongoing basis during the study conduct by an internal GSK Safety Review Team (SRT).

An internal GSK Safety Review Committee (iSRC), independent of the study team, will maintain governance of the study and will periodically review all available data in an un-blinded manner with a focus on key safety parameters. A Therapeutic Area (Immuno-Inflammation) Data Assessment Committee (TA DAC), independent of the study team, will periodically review un-blinded efficacy data and at the interim analysis will advise

the iSRC on adaptive design changes should such changes be required. An iSRC charter details the activities of these committees, including when and which data will be reviewed, how the integrity of the study will be maintained, and the membership of both committees. Once approximately half of the planned subjects (i.e.: approximately 35 subjects) have completed their Week 24 assessments, a formal interim analysis will take place. Appropriate available safety and efficacy data will be included in the interim analysis. The main purpose of the interim analysis is to assess the safety and tolerability of the study drugs. In addition, preliminary efficacy data will be evaluated. . Following the interim analysis, a number of actions could be mandated by the iSRC: the study may continue as planned; one or more treatment arms may be dropped; the number of subjects in some or all treatment arms may be increased following sample size re-estimation, up to a maximum of 120 subjects in the study.

4.2. Treatment Arms and Duration

Approximately 70 subjects will be recruited into the study initially. Withdrawals may be replaced. At Day 0, subjects will be randomized 1:2:2:2 to one of the four treatment arms below.

1. Placebo Arm: Approximately 10 subjects will receive belimumab placebo weekly subcutaneous injections to Week 52 and rituximab placebo infusions at Weeks 8 and 10.
2. Belimumab Monotherapy Arm: Approximately 20 subjects will receive 200 mg weekly subcutaneous injections of belimumab to Week 52 and placebo rituximab infusions at Weeks 8 and 10.
3. Co-administration Therapy Arm: Approximately 20 subjects will receive belimumab 200 mg SC weekly for 24 weeks followed by weekly placebo belimumab injections to Week 52 with rituximab 1,000 mg intravenously at Weeks 8 and 10.
4. Rituximab Monotherapy Arm: Approximately 20 subjects will receive 1,000 mg IV rituximab infusions at Weeks 8 and 10 and weekly subcutaneous injections of placebo belimumab to Week 52.

The subjects will be stratified based on their baseline disease activity severity [ESSDAI 5-12 (moderate) vs. ESSDAI >12 (severe)] ensuring that within each disease severity there is an allocation across all treatment groups.

The total number of subjects recruited will be determined through an ongoing review of the data and sample size re-estimation. Following interim analysis, a number of actions could be taken: the study may continue as planned; one or more treatment arms may be dropped; the number of subjects in some or all treatment arms may be increased following sample size re-estimation, up to a maximum of 120 total subjects in the study where up to a maximum of 25, 45, 30 and 20 will be randomized to placebo, belimumab monotherapy, co-administration therapy and rituximab monotherapy respectively. The randomization ratio will vary dependent on the number of treatment arms continuing following the interim analysis.

4.3. Follow up Periods

4.3.1. General Follow up Period

Subjects in all arms will receive investigational product (IP) until Week 52 (completion of the treatment phase). All subjects will enter a 16-week general follow-up period after the Week 52 visit or after discontinuation if a subject discontinues IP and withdraws from the treatment phase visits prior to Week 52. Assessments to be performed are included in the Time and Events Table, Section 7.1. During the general follow up period subjects will remain off of investigational product, endeavor not to change concomitant medication regimen, receive monthly safety follow up phone calls, and will return to the clinic for a site visit at the end of the general follow up period.

Monthly telephone calls for urine pregnancy test results, neurological questionnaire and to evaluate AEs, SAEs, and concomitant medications will be required during the 16-week general follow-up period.

4.3.2. Individualized Follow up Period

After completing the general follow-up period, subjects with CD 19+ B-cell levels below the lower limit of normal (or less than 90% of baseline, if baseline value was below LLN) will enter an individualized safety follow-up phase and return to the clinic for visits every 12 weeks with monthly calls between visits to evaluate subjects for any SAEs related to IP or study participation, fatal SAEs, and designated AESIs (i.e., infections, malignancies, or depression, suicide/self-injury), and to check concomitant medications. Each subject will be followed until either “normalization” of CD 19+ B cell count occurs or, at the investigator’s discretion the subject starts receiving disease modifying therapy that may affect B-cell numbers, or for up to a maximum of 2 years (i.e., up to Week 104) – whichever comes first. “Normalization” is defined as return of CD 19+ B cell count above LLN or within 10% of baseline (in cases where the baseline value itself was below LLN). When a decision is made for subjects to exit the individualized safety follow up phase, they will attend a final site visit within 28 days of that decision for final efficacy assessments to help explore the durability of any treatment response.

Subjects who prior to the Week 68 visit receive a disease modifying therapy that may affect B-cell numbers are not required to enter the IFU.

Finally, as this is an exploratory clinical trial and neither agent is licensed for Sjögren’s syndrome there are no plans to provide either agent following completion of the treatment phase of the study.

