- During the treatment and follow up phases (see Section 4.3.1 and Section 4.3.2), all study staff (which includes the investigator, sub-investigators, other site trial staff, and the subject) will remain blinded to central laboratory data that have the potential to unblind a subject's treatment assignment. Such data may include but is not necessarily limited to:
 - B-cell lymphocyte counts including results from flow cytometry
 - IgM and IgA levels

Refer to the central laboratory manual for additional information.

- The iSRC will perform safety reviews of laboratory data during the conduct of the study, as outlined within the iSRC charter.
- Sponsor open refers to those members of the iSRC and the TA DAC who are unblinded, as outlined in the iSRC charter. The GSK study team will remain blinded until the primary analysis (see Section 9.4.1) except for those in unblinded roles e.g., unblinded monitor for monitoring the pharmacy etc, as well as a restricted number of team members required for interpretation of data at the interim analysis (Section 9.3.2), as specified in the iSRC Charter.

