6. Subjects will enter the IFU if, following the general follow up period, their CD19+ B-cell levels remain below the lower limit of normal (or less than 90% of baseline, if baseline value was below LLN). During the IFU, subjects will be seen in the clinic every 12 weeks (\pm 7 days), with calls every 4 weeks (\pm 7 days) between visits to evaluate subjects for AEs & concomitant medications. Subjects will exit the IFU when: CD19+ B-lymphocyte counts are within normal range or 10% of baseline levels (if baseline < LLN), OR at the investigator's discretion the subject starts receiving disease modifying therapy that may affect B-cell numbers OR or for up to a maximum of 2 years (i.e., up to Week 104) – whichever comes first. Subjects exiting IFU period will attend a final visit (within 28 days of that decision) for final assessments (IFU Final Visit) as detailed in the Table.
7. Obtain samples post-dose only, within 10 minutes after end of infusion.
8. Both doses of rituximab/placebo will be administered in the clinic. Approximately 60 minutes prior to rituximab/placebo, subjects will receive orally an antipyretic and an antihistamine. At least 30 minutes prior to administration of rituximab/placebo, subjects will receive IV 100mg methylprednisilone . The 2nd rituximab/placebo administration at the Week 10 visit must be given 14 days (13-18 days, see SRM) after the first administration (given at the Week 8 visit). A patient alert card should be sent home with the subject following each dose of rituximab/placebo.
9. If urine test is positive, confirm with serum test. Pregnancy testing & contraception are required until 16 weeks post last administration of study treatment for those subjects who complete Weeks 46- 52 or withdraw from treatment prior to Week 8 dosing. Pregnancy testing and contraception are required for approximately 12 months after the administration of the final rituximab/placebo dose for the subset of subjects who discontinue treatment from Week 8 up to Week 46.
10. Subjects will receive a reminder phone call 48 hours prior to efficacy assessment visits to remind them that they should not be using certain symptomatic therapies prior to visit (see Section 4.1 of Study Reference Manual for details); in addition subjects should document their last use of symptomatic therapies in their self injection log book.

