7.4.1.1. Time Period and Frequency for Collecting AE and SAE Information

- AEs and SAEs will be collected from the start of Study Treatment through the general follow-up period (see Section 4.3 and the Time and Events Table in Section 7.1)
- Medical occurrences that begin prior to the start of study treatment but after obtaining informed consent may be recorded on the Medical History/Current Medical Conditions section of the eCRF.
- Any SAEs assessed as related to study participation (e.g., protocol-mandated procedures, invasive tests, or change in existing therapy) or related to a GSK product will be recorded from the time a subject consents to participate in the study up to and including any follow-up contact.
- During the individualized safety follow-up phase (if applicable, see Section 4.3 and the Time and Events Table in Section 7.1), only SAEs assessed as related to the investigational product or to study participation, fatal SAEs, and designated AESIs (i.e., infections, malignancies, and depression/suicidality/self-injury) will be collected.
- All SAEs will be recorded and reported to GSK within 24 hours, as indicated in [Appendix 7](#).
- Investigators are not obligated to actively seek AEs or SAEs in former study subjects. However, if the investigator learns of any SAE, including a death, at any time after a subject has been discharged from the study, and he/she considers the event reasonably related to the study treatment or study participation, the investigator must promptly notify GSK.

NOTE: The method of recording, evaluating and assessing causality of AEs and SAEs plus procedures for completing and transmitting SAE reports to GSK are provided in [Appendix 7](#).

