9.4. Key Elements of Analysis Plan

9.4.1. Primary Analysis and Follow Up Analysis

In addition to the interim analysis, there will be additional analyses for this study, corresponding to the primary analysis and the follow-up analyses. The primary analysis will occur after the data through the Week 52 visit (or withdrawal visit for those subjects who withdraw during double-blind treatment) for all subjects has been collected, verified and validated. The follow up analyses will occur after data through the 16-week generalized follow-up period and IFU periods for all subjects has been collected, verified and validated. All subjects and study site personnel (except the unblinded site pharmacist) will remain blinded until the follow up analyses have been completed.

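### Section 6.3 claims blinding to B-cell counts during the individualized follow-up, but entry to that phase, and in part exit from it, discloses the CD19+ category to site and subject

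*Protocol*

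**What the plan says.** **Entry.** Section 4.3.2 admits to the IFU, after the general follow-up, "subjects with CD 19+ B-cell levels below the lower limit of normal", with a threshold of 90% of baseline where baseline was already low. No other criterion for entry is given. Subjects who start a B-cell-affecting disease modifying therapy before Week 68 need not enter.

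**Exit.** There are three routes: normalization, such a therapy started at the investigator's discretion, or the maximum duration (Week 104). Normalization "is defined as return of CD 19+ B cell count above LLN or within 10% of baseline" where baseline was low. Footnote 6 of the Time and Events Table (Section 7.1) repeats the trigger: "CD19+ B-lymphocyte counts are within normal range or 10% of baseline levels (if baseline < LLN").

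**Blinding to laboratory data.** Section 6.3: "During the treatment and follow up phases (see Section 4.3.1 and Section 4.3.2), all study staff", the investigator and the subject included, "will remain blinded to central laboratory data that have the potential to unblind" a subject's treatment. B-cell counts head the list of such data. Footnote 2 of the Time and Events Table blinds sites to them from the end of screening.

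**Blinding to treatment.** Section 9.4.1 says subjects and site personnel, apart from the unblinded pharmacist, "will remain blinded until the follow up analyses have been completed". Those analyses include the IFU data.

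**What is collected in the IFU.** Under Section 7.4.1.1, "only SAEs assessed as related to the investigational product or to study participation, fatal SAEs, and designated AESIs" are collected (infections, malignancies, and depression/suicidality/self-injury). Section 4.3.2 adds a final visit with efficacy assessments to explore durability of response.

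**The concern.** A rule that acts on a concealed laboratory result discloses that result when the action is visible. IFU membership is visible: the site schedules the 12-weekly visits and the calls between them, and the subject attends. So the protocol states a property of the IFU phase that its own entry rule removes.

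Two kinds of IFU data rest on judgement made with that knowledge. First, a non-fatal SAE outside the designated AESIs is collected only if it is assessed as related to the product or to study participation, and the assessor knows that the subject entered with a low count. Section 9.4.2 makes investigator-reported relationship the main consideration in evaluating safety, which is the primary objective. Second, at the IFU Final Visit the treating physician scores ESSDAI and the subject rates dryness and other symptoms, both often knowing whether B cells have recovered. A reader relying on Section 6.3 would take these data as collected blind to B-cell status.

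**Working it through.** The protocol gives no figure to reproduce. The check sets the rules side by side, then asks what IFU status says about the arm.

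**Step 1: what status discloses.**

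| Event seen by site and subject | What it discloses |
|---|---|
| Called into the IFU | CD19+ below LLN, or below 90% of a low baseline |
| Not called in, no prior disease modifying therapy | CD19+ at or above that threshold |
| Released with no such therapy and before the maximum duration | CD19+ normalized |
| Released after such therapy or at the maximum duration | Normalization not implied |
| Not entered because of such therapy | Nothing about the count |

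The site knows when the last two rows apply, so every other case is informative. Footnote 2 blinds B-cell data only after screening, so the site can also tell from the screening value which branch of the threshold applied. The protocol describes no masking, such as one schedule for all subjects or a separate team for the IFU visits.

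**Step 2: when.** The general follow-up ends at 52 + 16 = Week 68 for completers. Subjects who stop early and decline further treatment-phase visits reach the decision sooner, 16 weeks after their last dose. From Week 68 to Week 104 is 36 weeks, or 36/12 = 3 scheduled visits.

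**Step 3: what this says about the arm.** The planned initial numbers are 10 placebo, 20 belimumab, 20 co-administration and 20 rituximab (Section 4.2). From allocation alone, P(rituximab-containing arm) = 40/70 = 57%. Let r, b and p be the IFU entry rates in the rituximab-containing, belimumab and placebo arms. Then

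P(rituximab-containing | IFU) = 40r / (40r + 20b + 10p).

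Setting this above 40/70 gives 120r > 80b + 40p, that is, r > (2b + p)/3. The protocol gives none of the three rates. Two sets, both **assumed**, show the consequence:

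- r = 0.7, b = 0.1, p = 0.02: 28 / (28 + 2 + 0.2) = 93%, above 57%.
- r = 0.3, b = 0.7, p = 0.02: 12 / (12 + 14 + 0.2) = 46%, below 57%.

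The second set cannot be ruled out from the text. In the belimumab arm the last dose is at Week 51, which is 68 − 51 = 17 weeks before the Week 68 visit. The last rituximab infusion is at Week 10, which is 68 − 10 = 58 weeks before it. Placebo entry is not fixed either: exclusion criterion 30 bars a low CD19+ count only after earlier B-cell depleting therapy, so other subjects may start below LLN and enter after a fall of just over 10%. Equal rates in all arms would leave the odds unchanged.

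So disclosure of the category is certain, while the shift in the odds of the arm has no derivable size and, for rituximab, no derivable direction.

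**Step 4: which data come after the disclosure.** The Week 24 comparison and Week 52 assessments come first. For completers so do the Week 68 assessments, because the deciding sample is due at that visit and its central result follows. What remains is the IFU safety reporting and the IFU Final Visit.

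**The case against.** The strongest reply is that little is lost.

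- Section 9.4.1 and the first bullet of Section 6.3 promise blinding to treatment, and IFU status identifies no arm. It cannot, for instance, separate co-administration from rituximab alone. This stands. Section 9.4.1 needs a cross-reference, not a retraction.
- A reader might infer that IFU entrants are recognizably rituximab-treated, so that the treatment blind is broken after Week 68. The documents do not support that. They give no recovery rates by arm, and plausible assumptions move the odds either way.
- Infections, malignancies, the depression/suicidality/self-injury group and all fatal SAEs are collected in the IFU whatever their assessed relationship, and these include the infection and malignancy risks tied to B-cell depletion. This stands and narrows the safety exposure to the remaining non-fatal SAEs. A reader might go on to infer that every IFU SAE must be collected. Targeted long-term collection is a legitimate choice, and the blinding inconsistency does not overturn it.
- Durability is listed as an endpoint at Week 52, Section 9.4.3 fixes estimates at Weeks 24 and 52, and IFU subjects are a subset selected after randomization. This stands: IFU Final Visit efficacy could not support a randomized comparison even if perfectly blinded.
- The central laboratory manual and the iSRC charter, not at hand, may govern who learns what and when. They could hide the count, but not the status from the people who run and attend the visits.

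None of this removes the conflict between Sections 4.3.2 and 6.3. Nor is it leftover wording: Appendix 15 shows that Amendment 6 extended the laboratory blind to both follow-up phases.

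**Conclusion.** The concern holds as a partial leak. Section 6.3 claims blinding to B-cell data in a phase whose entry rule, and one of whose exit rules, discloses the CD19+ category to site and subject. That follows from the text alone and needs no assumed rates.

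No numerical size is given for the shift in the odds of treatment, because the protocol supplies no entry rates. The figures in the working serve only to show that even the direction for rituximab is open.

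The reach is confined to the IFU: causality of non-fatal SAEs outside the designated AESIs, and with it whether they are collected, and ESSDAI and patient-reported scores at the IFU Final Visit. A reader might infer that the main efficacy results are compromised. They are not, since the disclosure comes after those assessments. The wording should be corrected, but the trial's main conclusions do not depend on it.

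**What to change.** 1. In Section 6.3, limit the claim of blinding to B-cell data to the period up to the IFU entry decision: Week 68 for completers, earlier for those who withdrew early. State that IFU status discloses the CD19+ category. Align footnote 2 of the Time and Events Table and add a cross-reference in Section 9.4.1.
2. Report IFU causality assessments and IFU Final Visit efficacy as not blinded to B-cell status.
3. Optionally, have efficacy and causality entries for the end of the general follow-up completed before IFU status is communicated. The gain is small, because the CD19+ result normally follows that visit.

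The cost is a few sentences in the protocol and a label in the reporting. No visits, subjects, follow-up rules or safety collection change. The price is a less favourable, but accurate, statement about blinding in the IFU.
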